The Investigational NOR-SOLIDARITY protocol

[figure not shown]
Project title

The NOR Solidarity multicenter trial on the efficacy of different anti-viral drugs in SARS-CoV-2 infected patients

Short title: The NOR-SOLIDARITY trial

EudraCT no: 2020-000982-18

Version: 12 2020-06-11

CONFIDENTIAL

This document is confidential and the property of the study group. No part of it may be transmitted, reproduced, published, or used without prior written authorisation.

STATEMENT OF COMPLIANCE

This document is a protocol for a clinical research study. The study will be conducted in compliance with all stipulations of this protocol, the conditions of Regional Ethic committee approval and the latest version of the Helsinki Declaration.

This protocol describes a multicenter add-on trial that is part of and based on the global WHO COVID-19 core protocol. The aim of the WHO COVID-19 core protocol is to evaluate and compare four different antiviral treatment regimens on in-hospital mortality in moderate and severe COVID infected patients. This multicenter add-on trial will be a separate and independent trial but will use the global level randomization and contribute to report endpoints and adverse events to the global trial.

Synopsis of the protocol

Terminology: The novel coronavirus-induced disease first described in 2019 in China is designated COVID-19 (or COVID), and the pathogen itself (an RNA virus) is SARS-coronavirus-2 (SARS-CoV-2). The Norwegian study that is an adapted WHO-study and follows the WHO protocol whilst also analyzing additional factors is referred to as the NOR-SOLIDARITY study. Standard of Care will be referred to as SoC.

Background: In early 2020 there were no approved anti-viral treatments for COVID, and WHO expert groups advised that four re-purposed drugs, Hydroxychloroquine, Remdesivir, Lopinavir with Ritonavir and Interferon (β 1a) should be evaluated in an international five-arm randomized trial where the fifth arm is SoC. The NOR-SOLIDARITY study started analyzing the effects of Hydroxychloroquine and Remdesivir initially and may open for a fourth arm.

Notification: Hydroxychloroquine was removed as treatment option by the steering committee on June 8th 2020 due to lack of evidence confirmed both in internal WHO interim analyses and an external report from the Recovery study. Thus, from this date, June 8th 2020, NOR-Solidarity allocate patients only to SoC and SoC+ Remdesivir.

Patient enrolment and randomization: This will be carried out online via a database created for this purpose by the WHO. Adults (age \geq 18 years) recently hospitalized, or already in hospital, with definite COVID and, in the view of the responsible doctor, no contra-indication to any of the study drugs will be randomly allocated between

- Local SoC alone,
OR local SoC plus
- Remdesivir

Data reported before randomization via the WHO database:

- Hospital and randomizing doctor
- Confirmation that informed consent has been obtained
- Patient identifiers, age and sex
- Patient characteristics (yes/no): current smoking, diabetes, heart disease, chronic lung disease, chronic liver disease, asthma, HIV infection, active tuberculosis.
- COVID-19 severity at entry (yes/no): shortness of breath, being given oxygen, already on a ventilator, and, if lungs imaged, major bilateral abnormality (infiltrations/patchy shadowing)
- Whether the study drug is currently NOT AVAILABLE at the hospital.

Inclusion criteria

1. Adult patients, 18 years and older
2. Confirmed SARS-CoV-2 infection by PCR
3. Admitted to the hospital ward or the ICU
4. Subjects (or legally authorized representative) provide informed consent prior to initiation of the study
5. No anticipated transfer within 72 hours to a non-study hospital

Exclusion criteria

1. Severe co-morbidity with life expectancy $<$ 3 months according to investigators assessment
2. ASAT/ALAT $>$ 5 times the upper limit of normal
3. Acute co-morbidity within 7 days before inclusion such as myocardial infarction
4. Known intolerance to the study drug
5. Pregnancy or breast feeding
6. Any reason why, in the opinion of the investigators, the patient should not participate

7. Participation in a potentially confounding drug or device trial during the course of the study
8. Already receiving any of the current study drug(s)
9. Patients on concomitant medications, which is part of the list of prohibited medications have to be excluded from the current study.

Prohibited medication:

Haloperidol, carbamazepine, phenytoin, rifampin, phenobarbital, isoniazid, pyrazinamide, nevirapine, ritonavir, sodium valproate/valproic acid

Drug safety: Suspected unexpected serious adverse reactions (SUSARs) that are life-threatening (e.g. anaphylaxis, Stevens-Johnson syndrome, aplastic anemia, or any other life-threatening condition in the opinion of the investigator) must be reported within 24 hours of being diagnosed, without waiting for death or discharge.

Daily blood samples will be taken, including estimated GFR, electrolytes and urea.

Outcomes: The primary outcome is all-cause in hospital mortality compared to standard of care. The major secondary outcomes are duration of hospital stay, time to first receiving ventilation (or intensive care), viral clearance, kidney failure, myocardial failure, co-infections, organ dysfunction, quality of life after 3 months, Inflammatory and anti-inflammatory mediators, markers of extracellular matrix remodeling, markers of endothelial activation and markers of platelet activation.

Data monitoring: A Data and Safety Monitoring Committee will keep the accumulating drug safety results and major outcome results under regular review.

Adaptive design: The WHO may decide to add novel treatment arms while the trial is in progress. Conversely, the WHO may decide to discontinue some treatment arms, especially if the Global Data and Safety Monitoring Committee reports, based on interim analyses, that one of the trial treatments definitely affects mortality.

Data security: Patient information will be encrypted and held securely by the WHO and sponsor. Those analyzing it will use only anonymized data, and no identifiable patient details will appear in publications.

Table of Contents

1 Investigators and facilities	8
1.1 Study locations and principal investigators	8
1.2 Study Management	9
1.3 Monitor	9
2. Background and objectives	10
2.1 Background Information	10
2.1.1 Clinical trial rationale	10
2.2 Target audience	11
2.3 Study design	11
4 Study population	14
4.1 Inclusion criteria (as described in WHO COVID 19 core protocol)	14
4.2 Exclusion criteria	14
4.3 Prohibited concomitant medication	14
4.4 Baseline characteristics	14
5 Study products and study drug regimes	15
5.1 Remdesivir	15
5.2 Medical side effects and management of Remdesivir	15
5.2.1 Remdesivir and renal function	16
5.2.2 Remdesivir and prohibited concomitant medication	16
5.3 General information on intervention drugs	16
6 Drug discontinuation and patient withdrawal	16
7 Study assessments and procedures	17
7.1 Clinical variables	17
7.2 Case report form and patient numbers	17

1.3 Monitor

The study will be monitored by clinical study monitors located at the University Hospital of North Norway, St Olav's Hospital, Haukeland University Hospital and Oslo University Hospital.

All sites will be visited and/or contacted by phone on a regular basis by the monitor, who will verify that informed consent process, reporting of adverse events and other safety data, adherence to protocol, maintenance of required regulatory documents, facilities and equipment and data completion on the case report forms, including source data verification are up to standard. The details of the monitoring, e.g. the processes, equipment and data to be checked, will be described in a study specific monitoring plan.

2. Background and objectives

2.1 Background Information

Infectious diseases are the single biggest cause of death worldwide. New infectious agents, such as the SARS, MERS and other novel coronavirus as well as influenza viruses, all represent a threat and disease burden to the society and health facilities. Influenza epidemics and pandemics worldwide continue to challenge public health and health care systems. The pandemic in 2009-2010 resulted in 100.000-400.000 deaths, affecting not only elderly individuals and individuals with co-morbidities, but also children and young adults (1). The present pandemic with COVID-19 is expected to result in a high number of critically ill patients in need of hospitalization and respiratory support, and an unknown proportion of patients who inevitably will die. As of today, no specific treatment of COVID-19 has been established. To this end, Remdesivir is the only treatment option that directly inhibits SARS-CoV-2 RNA polymerase and has been shown to inhibit virus replication *in vitro*. It has also been shown to have protective effects against the familiar coronavirus MERS (2), and notably, both preclinical experiments and case reports suggest that Remdesivir could have beneficial effects in COVID 19 (3, 4). For additional background information about coronaviruses and the Mechanism of action of Remdesivir see sections 1.1.2, 1.2.2, and 3.1.1 of the Remdesivir Investigators Brochure (5). Another promising treatment option is hydroxychloroquine which seems to be effective in limiting the replication of SARS-CoV-2 *in vitro* at least partly by interfering with the pH-dependent endosome-mediated viral entry, and its potential effect in COVID-19 has been suggested by six publications (6). Clinical experience with the use of neuraminidase inhibitors demonstrated that prompt treatment probably represents the most effective strategy for the management of influenza epidemics (7). It is conceivable that a similar early treatment strategy is also necessary in COVID 19 patients and is applicable to other drug therapies, but so far, no data exist to support this assumption.

The WHO COVID 19 core protocol has been designed to prospectively collect clinical data globally, and rapidly evaluate and conclude whether different anti-viral treatment regimens can reduce in-hospital mortality. Along with this, separate and independent add-on trials will use the global level randomization centre and contribute to report endpoints and adverse events as encouraged by the WHO (8).

Notification: Hydroxychloroquine was removed as treatment option by the steering committee on June 8th 2020 due to lack of evidence confirmed both in internal WHO interim analyses and an external report from the Recovery study. Thus, from this date, June 8th 2020, NOR-Solidarity allocate patients only to SoC and SoC+ Remdesivir.

2.1.1 Clinical trial rationale

The rationale for the study is to test whether available anti-viral drugs with the potential to inhibit SARS-CoV-2 (at this moment only Remdesivir) have any clinical effect on COVID-19 infected patients.

Knowledge from this study will hopefully contribute to the clarification of whether Remdesivir is beneficial or not and if early Remdesivir intervention is needed to have any beneficial effects. This is important knowledge and highly relevant for future treatment of COVID-19 infected patients.

Data from the study will also provide increasing knowledge of the pathogenesis of severe COVID-19 infection and in particular, which molecular pathways and biomarkers that characterize those patients that need ICU management and those that could be managed at the hospital ward.

2.2 Target audience

Departments of Infectious Diseases and ICUs at hospitals in Norway treating COVID-19 infected patients are invited to participate in this study and contribute with data to a centralized database. We encourage all centres to contribute to this effort. In all cases, a proportionate case report form (a web-based electronic “eCRF”) will be completed.

2.3 Study design

The NOR-SOLIDARITY study is an adaptive, randomized, open clinical multicentre trial to evaluate the safety and efficacy of possible therapeutic agents in hospitalized adult patients diagnosed with COVID-19. See the WHO COVID-19 core protocol (Appendix 1) for the core trial design. This multicentre add-on trial will follow the WHO core protocol version 10 dated 22.03.2020 but will add additional secondary and exploratory endpoints.

Adults (age ≥ 18 years) recently hospitalized, or already in hospital, with definite COVID and, in the view of the responsible doctor, no contra-indication to any of the study drugs will be randomly allocated between

- Local standard of care alone,
OR local standard of care plus
- Remdesivir (one intravenous loading dose, then daily infusions for altogether 10 days)

The primary objective of the trial is to investigate the effect of Remdesivir on all-cause in-hospital mortality compared to standard of care.

Patients will be followed daily during hospitalization, after 28 days by telephone/sms and then by an outpatient clinical visit after 3 months.

In the core protocol follow-up data are only collected at discharge. In this protocol subjects will additionally be assessed for efficacy and safety both during hospitalization and after hospitalization.

In addition to the global independent data and safety monitoring board (DSMB) as described in the core protocol, a national DSMB will monitor the safety and risk-benefit of the trial interventions in the Norwegian population.

[figure not shown]

Figure 2: The Investigational NOR-SOLIDARITY protocol

3 Objectives and endpoints

Objectives	Endpoints (Outcome measures)
Primary (in line with WHO core protocol)	
To investigate the effect of Remdesivir on all-cause in-hospital mortality compared to standard care.	All-cause in-hospital mortality
Secondary (in line with WHO core protocol)	
Assess the effect of Remdesivir on hospital duration, receipt of ventilation or intensive care, and to identify any serious adverse reactions.	During hospitalization 
 • Receipt of mechanical ventilation • Time to first receiving and duration of mechanical ventilation • Receipt of intensive care • Duration of intensive care • Occurrence of Suspected Unexpected Serious Adverse Reactions (SUSARs)
Secondary (as addition to the WHO core protocol)	
Assess the effect of Remdesivir on 28 days mortality, viral clearance, kidney and myocardial failure, co-infections, organ dysfunction and health-related Quality of Life.	Assessed during hospitalization 
 • Viral clearance as assessed by SARS-CoV-2 PCR in oropharyngeal specimens during hospitalization • Occurrence of kidney failure (eGFR <40 mL/min) • Occurrence of myocardial involvement assessed by biochemical markers as well as echocardiography measuring left ventricular ejection fraction within the first week • Occurrence of co-infections (super infections with bacteria, fungi and other virus) Assessed after 28 days 
 • Overall survival • Patient reported respiratory health status by CAT (Chronic Obstructive Pulmonary Disease (COPD) assessment Test) score Assessed after 3 months 
 • Occurrence of systolic and diastolic cardiac dysfunction and level of remodelling assessed by echocardiography and biochemical markers • Occurrence of pulmonary dysfunction and level of fibrosis assessed by spirometry and thoracic CT scan • Health related quality of life assessed by the RAND 36-item Short Form Health Survey (SF-36) item scores and the 5-dimension EuroQol (EQ-5D) questionnaires index value.
Exploratory (as addition to the WHO protocol)	

Assess the effect of Remdesivir on biomarkers and its safety.	Biomarkers during hospitalization and after 3 months 
 • Inflammatory and anti-inflammatory mediators as assessed in serum and plasma • Markers of extracellular matrix remodelling • Markers of endothelial activation • Markers of platelet activation • Cellular immunity • Prognostic biosignatures (RNA) • Gut microbiota assessed by rectal swab • Pharmacokinetics during hospitalization • Adverse events during hospitalization
---	--

4 Study population

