10.5.2 Secondary analyses

Between group comparisons will be performed for the primary variable on the per-protocol population in addition to secondary efficacy endpoints on both efficacy populations (ITT and PP populations).

The between-group comparisons for secondary variables will be tested as for the primary variable where applicable and additional analyses will be performed based on the following methods (but not limited to):

- Continuous secondary variables will be subject to repeated measures mixed models or appropriate non-parametric alternatives
- Binary response variables will be analysed using logistic regression (possibly adjusting for within-subject dependencies by generalized estimating equations or mixed models) or chi-square/Mantel-Haenszel tests
- Time-to-event variables will be analysed using the Kaplan-Meier method and comparisons between the two groups will be performed using the log rank test, Cox regression analyses or appropriate parametric models such as the gamma or Weibull model.

Unless otherwise specified, all statistical hypotheses will be tested as the primary variable, i.e. with an assessment of superiority of the estimated difference between the groups. All efficacy analyses will be presented with the results from the hypothesis testing (by p-value) in addition to estimates and 95% confidence limits of the treatment effect.

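### The SF-36 part of the 3-month quality-of-life endpoint is set at item level: read literally, up to 36 tested results for one construct and no overall SF-36 result

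*Protocol*

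**What the plan says.** The secondary objective that the protocol adds to the WHO core protocol (section 3) ends with "organ dysfunction and health-related Quality of Life", named as one construct. The synopsis lists "quality of life after 3 months" among the major secondary outcomes.

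The matching endpoint in section 3, assessed after 3 months, has two parts. The first is "Health related quality of life assessed by the RAND 36-item Short Form Health Survey (SF-36) item scores". The sentence then continues "and the 5-dimension EuroQol (EQ-5D) questionnaires index value". No SF-36 scale or summary score is named in section 3 or elsewhere in the protocol.

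Section 10.5.2 covers the analysis. It plans comparisons of "secondary efficacy endpoints on both efficacy populations (ITT and PP populations". For continuous variables it says: "Continuous secondary variables will be subject to repeated measures mixed models or appropriate non-parametric alternatives". On reporting it says: "All efficacy analyses will be presented with the results from the hypothesis testing (by p-value", together with estimates and 95% confidence limits. Section 10.4 leaves the detail of the analyses to a separate SAP.

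**The concern.** The protocol fixes the level at which the SF-36 is measured, and that level does not match the objective. The objective asks one question about health-related quality of life. The neighbouring instruments in section 3 are each reduced to one number: the COPD assessment test to a score and EQ-5D to an index. Only the SF-36 is left at the level of its items.

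Two things follow if the text is applied as it stands. First, with a p-value for every efficacy analysis, the SF-36 can produce as many tested results as it has items, with none marked as the key one and no multiplicity control tied to them. Some nominal difference then becomes likely by chance. Second, nothing says how a mixture of item results would be turned into an answer on quality of life, so the SF-36 could be reported through whichever items happen to differ.

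**Working it through.** **Inputs**
- Number of items, k = 36. It comes from the instrument's name in section 3, "RAND 36-item Short Form Health Survey". That each item would be a tested variable is an inference from the endpoint wording plus section 10.5.2.
- One further variable in the same endpoint: the EQ-5D index value.
- Level per test, α. Section 10.5.2 states none for secondary endpoints; its 95% confidence limits point to 5%. The 2.5% level in section 10.1 belongs to the mortality and intensive-care sample sizes. Both are shown.
- Correlation between items: not given, so the range is shown.

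**The plan's own figures.** The protocol gives no test count, standard deviation, effect size or power for quality of life, so there is no such figure to reproduce. Its target of 406 per group concerns receipt of intensive care. With 26% against 16%, two-sided 2.5% and 90% power, n = (z₁ + z₂)² × [0.26 × 0.74 + 0.16 × 0.84] / 0.10² = 405.6, which rounds up to 406. No quality-of-life input enters it.

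**Formulas.** With no true effect:
- expected number of nominally significant results = kα, whatever the correlation;
- chance of at least one under independence = 1 − (1 − α)^k.

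**Results**

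| Variables tested | k | α | Expected | At least one, if independent |
|---|---|---|---|---|
| SF-36 items | 36 | 5% | 1.8 | 84.2% |
| Items plus EQ-5D index | 37 | 5% | 1.85 | 85.0% |
| SF-36 items | 36 | 2.5% | 0.9 | 59.8% |
| Items plus EQ-5D index | 37 | 2.5% | 0.925 | 60.8% |
| Eight scale scores (assumed number, not in the protocol) | 8 | 5% | 0.4 | 33.7% |
| One SF-36 summary plus EQ-5D index | 2 | 5% | 0.1 | 9.8% |

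**Effect of correlation.** For two-sided tests with jointly normal statistics, independence is the worst case (Šidák's inequality), so 84.2% is a ceiling for 36 items at 5%. The floor is 5%, reached if all items moved together perfectly. Answers to one questionnaire should be positively correlated, so the true value lies between these. The documents do not allow it to be placed more closely. The expected count of 1.8 does not change with correlation.

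**Two populations.** Section 10.5.2 asks for both ITT and per-protocol comparisons, so 36 items would give 72 p-values and 72 × 0.05 = 3.6 expected. The two sets share most of their patients, so this adds little independent chance of error and is not counted in the headline.

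**The case against.** The strongest case on the other side has four parts.

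- *Item scores may be loose wording for the instrument's scale scores, and scoring detail belongs in the SAP.* The wording may well be loose. But the protocol does not stay silent here: it states a level of measurement. A SAP that used scale scores would depart from the endpoint as written, and a SAP that followed the endpoint would compare items. The correction therefore belongs in section 3. The scoring algorithm itself can stay in the SAP.
- *Quality of life is not defined by SF-36 items alone.* This stands. A reader who stops at the SF-36 half of the sentence might infer that the trial has no overall quality-of-life measure. The same sentence names the EQ-5D index, which is one. The point is confined to the SF-36 part.
- *The protocol nowhere says that 36 tests will be run.* This also stands. A reader might infer a plan to test every item; the text supports only an upper count under a literal reading.
- *Section 10.5.2 does not force items into a model for continuous data.* Correct. A reader might infer that ordinal answers would be treated as continuous, but the section allows non-parametric alternatives and does not limit itself to the methods listed. No complaint is made on that score.

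It is also tempting to claim a loss of power because single items are noisy. The protocol gives no standard deviation or effect size for quality of life, so no such loss can be shown from it.

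**Conclusion.** The point holds as a minor one. Section 3 sets the SF-36 part of a secondary endpoint at item level while its objective names one construct and its companion measure is a single index. Applied literally with section 10.5.2, that gives up to 36 tested results, 1.8 of them expected to be nominally significant at 5% with no true effect. The chance of at least one is at most about 84%, reached only under independence.

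This rests on three assumptions: every item is compared, each at 5%, and the multiplicity adjustment in section 10.1 does not extend to quality of life, as nothing in the protocol says that it does. At 2.5% per test the figures fall to 0.9 expected and a ceiling of 59.8%.

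A reader might infer that the trial's quality-of-life conclusion as a whole is unsound. The documents do not support this: the EQ-5D index stands, and the primary analysis and the sample size do not depend on the SF-36.

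**What to change.** In section 3, replace item scores by the RAND-36 scale or summary scores obtained with the instrument's standard scoring. State which of these, or the EQ-5D index, is the key quality-of-life measure at 3 months. Say that item results are descriptive only, and add a short exception in section 10.5.2 so that its rule of a p-value for all efficacy analyses does not reach them. Which scales to name is for the sponsor; nothing in the protocol favours one over another.

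The questionnaire, the data collected and the visit schedule stay the same, so the cost is a few words in two sections. The small downside is that item-level results are no longer formally tested; they can still be tabulated.
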